3.4 SAMPLE SIZE CONSIDERATIONS

This is an exploratory study, therefore the sample sizes listed below are not based on a formal statistical estimation (sample size or power calculation are not required) but are considered to be adequate to meet the objectives of the study. A sufficient number of subjects will be initially screened for enrolment in both parts to ensure that the planned sample size is achieved.

In part 1, the dose escalation phase, approximately 11 to 24 patients in total will be enrolled, covering 5 or more dose levels. If more than 5 dose levels are required these numbers may increase proportionally.

In part 2, the dose expansion phase, approximately 18 patients will be enrolled to each of the 3 groups of patients with pre-defined advanced tumours of different types (up to 54 patients total)

There will be the potential to add 1 or more further groups to the dose expansion phase where the addition of such a group is thought to have efficacious potential. Any such groups will also aim to recruit 18 patients.

In total, it is anticipated that with 3 dose expansion groups, that up to 78 eligible patients will be enrolled. Should the dose expansion phase recruit additional groups as outlined above, this total will increase by up to 18 patients for each group added.

3.5 RANDOMISATION

As an open label design, there will be no randomisation for this study in either the dose escalation or dose expansion parts.

4 STUDY VARIABLES AND COVARIATES

4.1 PRIMARY VARIABLES

The primary endpoints are as follows:

Part 1: Dose Escalation:

- Number of patients with a DLT;
- Number of patients with ≥ 1 related AE;
- Number of patients discontinuing study treatment due to related AEs.

The RP2D will be determined at the conclusion of Part 1.

Part 2: Dose Expansion

- Progression free survival (PFS) based on RECIST v1.1 as assessed by the Investigator.

4.2 SECONDARY VARIABLES

The secondary endpoints of the study are the PK profile, as well as tumour response.

- PK parameters of OMO-103

- C_{\min} Minimum observed concentration;
 - C_{\max} Maximum observed concentration;
 - t_{\max} Time to maximum observed concentration;
 - $t_{1/2}$ Terminal elimination half-life;
 - AUC_{0-t} Area under the concentration-time curve (AUC) from the time of administration to the time of the last measurable concentration;
 - $AUC_{0-\infty}$ AUC extrapolated to infinity;

 - Additional PK analyses will be performed as deemed necessary upon review of the data.
- RECIST v1.1 criteria (see Protocol section **Error! Reference source not found.2**).
 - The scores and changes from Day 0 in QoL Questionnaire scores.

4.3 EXPLORATORY VARIABLES

Exploratory endpoints of the study are the PD profile.

Supporting study variables include biomarkers and Myc expression measurement. Additional biomarkers may be added if deemed relevant.

5 DEFINITIONS AND DERIVED VARIABLES

Product/IMP: Product/IMP is taken to mean the Myc Inhibitor OMO-103 administered intravenously.

Baseline: Unless stated otherwise, baseline is defined by subject and by variable as the last non-missing value (including repeat/unscheduled assessments) before the first use of IMP.

Protocol Deviation: a deviation related to study inclusion or exclusion criteria, conduct of the trial, subject management or subject assessment. This refers to any change, divergence, or departure from the study design or procedures defined in the protocol. Protocol deviations captured in the CRF will be reviewed on a regular basis during the study and discussed at the Data Review Meeting (DRM) before Database Lock (DBL). In addition, any deviations identified during the DRM will be discussed and included in the database as necessary. All protocol deviations within the study database will be classified as either 'Major' or 'Minor' prior to DBL, details of which will be included within the Protocol Deviations log within the CTMS and a protocol deviation listing.

6 ANALYSIS SETS

Membership of the analysis sets will be reviewed during the DRM and agreed prior to DBL. These will be reviewed by the Sponsor, Study Statistician, PK Analyst (PKS only) and Project Manager and included within the DRM minutes.

6.1 ALL PATIENTS SET (APS)

All subjects who were enrolled and not screening failures at Day 1 will constitute the All Patients Set. Subjects deemed eligible on Day 1 who do not partake in any IMP use will be listed and summarised for subject disposition only.

This analysis set will be used for study disposition and analysis set listings and summaries.

6.2 SAFETY SET (SAF)

All subjects in the APS who receive at least one dose of IMP will be included in the Safety Set.

This analysis set will be used for baseline and safety summaries as well as for all study listings.

6.3 FULL ANALYSIS SET (FAS)

All subjects within the SAF who record either a primary or secondary endpoint will be included in the Full Analysis Set.

This analysis set will be used for efficacy tables and some safety summaries.

6.4 PK SET (PKS)

Subjects from the SAF population will be assigned to the PK Set where they comply with the following criteria:

- Do not use a concomitant medication which renders the concentration profile unreliable;
- Have at least one sample with concentration above the lower limit of quantification (LLOQ);
- Do not violate the protocol in such a way that may invalidate or bias the results (major protocol deviation).

This analysis set will be used for summaries and statistical analyses of the PK data.

6.5 PER PROTOCOL SET (PPS)

All subjects within the FAS who complete the study without a major protocol deviation adjudged in the DRM to potentially affect any endpoint of the study will be included in the Per Protocol Set.

A PP analysis will only be performed for the dose expansion groups.

This analysis set will be used for efficacy tables.

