1 INTRODUCTION

1.1 GENERAL

This statistical analysis plan (SAP) describes the statistical methods to be used during the reporting and analyses of data and should be read in conjunction with the study protocol and case report form (CRF).

This version of the plan has been developed using the current approved protocol amendment version Final v2.0 dated 18 November 2021 and annotated CRF version dated 19 July 2021. Any further changes to the protocol or CRF will be reviewed for potential impact on the SAP which will be amended if it is deemed necessary.

Draft versions of the SAP will undergo review by the Statistical Reviewer, Statistical Programmer, Project Manager, Medical Writer, Principal Investigator and the Sponsor representative. The analysis plan will be finalised and approved by the Sponsor prior to Database Lock (DBL).

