11.1 SUBJECT DISPOSITION

The subject disposition table will summarise the following data:

- The number of subjects receiving IMP under each dose level
- The number (%) of subjects who withdrew from the study and the associated reasons for withdrawal and timing of withdrawal.
- The number (%) of subjects in each analysis set

Screening and study completion/termination data (including informed consent information) will also be listed. A listing of all protocol deviations will be presented including major/minor classification. A data classification. A data listing presenting subject eligibility for each analysis set and the reason for exclusion from an analysis set will also be presented.

Disposition data will be summarised and listed using the All Patients Set (APS) population.

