11.3 EFFICACY ANALYSES

The primary efficacy endpoint of the study will be:

- Anti-tumour activity will be assessed by PFS using RECIST v1.1 assessed by the Investigator.

Secondary endpoints are:

- DOR
- DCR
- TTR
- TTP
- ORR

- OS (only Part 2).

All efficacy endpoints will be summarised and analysed descriptively, using the FAS and SAF populations. Kaplan Meier plots will be presented for time to event endpoints. Waterfall plots will be presented for RECIST data. The primary efficacy analysis will be repeated using the PP set.

Quality of Life Questionnaire:

Absolute values and change from baseline for total score will be presented using descriptive statistics for QoL Questionnaire scores. Overall there are 30 questions.

Only physical, emotional, fatigue and global related scores will be summarized.

Physical Functioning related questions are: Q1, Q2, Q3, Q4, Q5.

Emotional Functioning related questions are: Q21, Q22, Q23, Q24.

Fatigue relates questions are: Q10, Q12, Q18.

Global questions are: Q29, Q30.

Grouped scores for physical, emotional, fatigue, global scales and total scores will be normalised to the range 0-100 prior to being summarised.

All questions with the corresponding scores will be listed.

Other analysis:

- OMO-103 dosing will be summarised and listed using the SAF.

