14.2 Efficacy Data

14.2.1 Efficacy parameters

Table 14.2.1.1	Summary of PFS	Safety Set
Table 14.2.1.2	Summary of PFS	Full Analysis Set
Table 14.2.1.3	Summary of PFS	Per Protocol Set <Part 2 only>
Table 14.2.2.1	Summary of Efficacy parameters, DCR, ORR, OS, TTP, TTR and DOR	Safety Set
Table 14.2.2.2	Summary of Efficacy parameters, DCR, ORR, OS, TTP, TTR and DOR	Full Analysis Set
Table 14.2.2.3	Summary of Efficacy parameters, DCR, ORR, OS, TTP, TTR and DOR	Per Protocol Set <Part 2 only>
Table 14.2.5	Dosing of OMO 103-01	Safety Set
Table 14.2.6	Change from Baseline: Quality of Life Questionnaire	Safety Set
Figure 14.2.6.1	Kaplan-Meier Plot of Time from Start of IMP to TTP	Full Analysis Set
Figure 14.2.6.2	Kaplan-Meier Plot of Time from Start of IMP to TTP	Per Protocol Set <Part 2 only>
Figure 14.2.7.1	Kaplan-Meier Plot of Time from Start of IMP to TTR	Full Analysis Set
Figure 14.2.7.2	Kaplan-Meier Plot of Time from Start of IMP to TTR	Per Protocol Set <Part 2 only>

I4.3 Safety Data**I4.3.1 Adverse Events**

Table I4.3.1.1	Summary of Treatment Emergent Adverse Events	Safety Set
Table I4.3.1.1a	Summary of Treatment Emergent Adverse Events – Event Count	Safety Set
Table I4.3.1.2	Summary of Treatment Emergent Adverse Events by System Organ Class and Preferred Term	Safety Set
Table I4.3.1.2a	Summary of Treatment Emergent Adverse Events by System Organ Class and Preferred Term – Event Count	Safety Set
Table I4.3.1.3	Summary of Treatment Emergent Adverse Events by Preferred Term	Safety Set
Table I4.3.1.4	Summary of Treatment Emergent Adverse Events by Severity, System Organ Class and Preferred Term	Safety Set
Table I4.3.1.5	Summary of Treatment Emergent Adverse Events by Relationship to IMP, System Organ Class and Preferred Term	Safety Set
Table I4.3.1.6	Serious Adverse Events	Safety Set
Table I4.3.1.7	Adverse Events Leading to Withdrawal	Safety Set

I4.3.2 Laboratory Safety

Table I4.3.2.1	Biochemistry Out of Normal Range Data	Safety Set
Table I4.3.2.2	Haematology Out of Normal Range Data	Safety Set
Table I4.3.2.3	Urinalysis Abnormal Values	Safety Set
Table I4.3.2.4	Autoimmune Values	Safety Set
Table I4.3.2.5	Frequency of Autoimmune Values	Safety Set

I4.3.3 ECG Data

Table I4.3.3.1	Statistical summaries of ECG parameters by visit	Safety Set
----------------	--	------------

I4.3.4 ECOG Performance Status

Table I4.3.4.1	Statistical summaries of ECOG status by visit	Safety Set
----------------	---	------------

I4.3.5 Vital Signs

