15 SHELLS FOR TABLES, FIGURES AND LISTINGS

The intended layouts for tables, figures and listings are presented. However, it may be appropriate to change the layouts, upon review of the data available, for completeness and clarity.

QCd output will be produced as Rich Text Format (.rtf) files for convenient inclusion in the CSR. The default tables, figures and listings (TFL) layout will be as follows:

Orientation	A4 Landscape								
Margins	
 
 Top:	2.54 cm	
 
 Bottom:	2.54 cm	
 
 Left:	2.54 cm	
 
 Right:	2.54 cm	
 
	Top:	2.54 cm	Bottom:	2.54 cm	Left:	2.54 cm	Right:	2.54 cm
Top:	2.54 cm								
Bottom:	2.54 cm								
Left:	2.54 cm								
Right:	2.54 cm								
Font	Courier New 9pt								
Headers (Centre)	Sponsor Protocol Number, TFL Number, Title, Analysis Set								
Footers (Left)	Source Listing, Date/Time TFL Generated, Page Number, i.e. Page x of y								

Listing shells are displayed within this document without the comments field but, should there be any comments recorded for the represented data, this field will be added to the listing. In addition, at the time of programming, footnotes will be added to the listing, table or figure as needed. All footnotes will be used for purposes of clarifying the presentation

Should the number of variables within a listing or table be too great to fit on one page without compromising clarity, then the variables will be split across multiple subsequent pages and key identifying variables replicated with these (i.e. subject number, visit etc). The differing pages will be identified using a sequential number which will follow the TFL title, i.e. xxxx - (1), xxxx - (2).

OMO-103-01
Table 14.1.1.1
Summary of Study Disposition - Part 1
All Patients Set

	Number of Subjects (%)
Consented	x
Screening Failures/Non-Runners	x
Dosed:	
0.48 mg/kg (Cohort 1)	x (x.x)
1.44 mg/kg (Cohort 2)	x (x.x)
.....	x (x.x)
Completed Study	x (x.x)
Early Withdrawal	x (x.x)
Reason for Early Withdrawal	
ADVERSE EVENT	x (x.x)
LOST TO FOLLOW-UP	x (x.x)
WITHDRAWAL BY SUBJECT	x (x.x)
STUDY TERMINATED BY SPONSOR	x (x.x)
PHYSICIAN DECISION	x (x.x)
PREGNANCY	x (x.x)
PROTOCOL VIOLATION	x (x.x)
DEATH	x (x.x)
OTHER	x (x.x)
Safety Set	x (x.x)
Full Analysis Set	x (x.x)
Per Protocol Set	x (x.x)

Source Listing: 16.2.1.2, 16.2.3.1; Produced: yyyy-mm-ddThh:mm - Page x of y
Percentages are based on the total number of dosed subjects.

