Programming note: A similar table will be presented for Part 2 (Dose expansion)

OMO-103-01
Table 14.1.2.1
Summary of Demographic and Baseline Information - Part 1
Safety Set

Parameter	Statistic	All Subjects (N=x)
Age (yrs)	n	x
	Mean	x.x
	SD	x.xx
	Min	x
	Median	x.x
	Max	x
Height (cm)	n	x
	Mean	x.x
	SD	x.xx
	Min	x
	Median	x.x
	Max	x
Weight (kg)	n	x
	Mean	x.xx
	SD	x.xxx
	Min	x.x
	Median	x.xx
	Max	x.x
Number of pre-treatments per patient	n	x
	Mean	x.xx
	SD	x.xxx
	Min	x.x
	Median	x.xx
	Max	x.x

Source Listing: 16.2.4.1; Produced: yyyy-mm-ddThh:mm - Page x of y

Percentages are based on the total number of subjects within the Safety Set.

Programming note: A similar table will be presented for Part 2.

[Continued overleaf...]

OMO-103-01
Table 14.1.2.1
Summary of Demographic and Baseline Information - Part 1
Safety Set

Parameter		Statistic	All Subjects (N=x)
Race:	BLACK OR AFRICAN AMERICAN	n (%)	x (x.x)
	AMERICAN INDIAN OR ALASKA NATIVE	n (%)	x (x.x)
	ASIAN	n (%)	x (x.x)
	NATIVE HAWAIIAN OR OTHER PACIFIC ISLANDER	n (%)	x (x.x)
	WHITE	n (%)	x (x.x)
	MIXED	n (%)	x (x.x)
	OTHER	n (%)	x (x.x)
Gender:	M	n (%)	x (x.x)
	F	n (%)	x (x.x)

Source Listing: 16.2.4.1; Produced: yyyy-mm-ddThh:mm - Page x of y
Percentages are based on the total number of subjects within the Safety Set.

*Programming note: A similar table will be repeated for 14.1.2.2 (FAS).
A similar table will be presented for Part 2.*

OMO-103-01
Table 14.2.1.1
Summary of Progression Free Survival (PFS) - Part 1
Safety Set

Parameter	Cohort	Statistic	
PFS	Cohort 1 (Dose 0.48 mg/kg) (N=x)	n	x
		Mean	x.x
		SD	x.xx
		Min	x
		Median	x.x
		Max	x
	Cohort 2 (Dose 1.44 mg/kg) (N=x)	n	x
		Mean	x.x
		SD	x.xx
		Min	x
		Median	x.x
		Max	x
	Cohort ...		
	Overall (N=x)	n	x
		Mean	x.x
		SD	x.xx
		Min	x
		Median	x.x
Max		x	

Source Listing: 16.2.7.1; Produced: yyyy-mm-ddThh:mm - Page x of y
Percentages are based on the total number of subjects within the Safety Set.

*Programming note: A similar table will be presented for Table 14.2.1.2 (FAS) and Table 14.2.1.3 (PPS)
All tables will be repeated for Part 2.*

OMO-103-01
Table 14.2.2.1
Summary of Efficacy parameters, DCR, ORR, TTP, TTR and DOR - Part 1
Safety Set

Parameter	Cohort	Component	Statistics	Result
DCR	Cohort 1 (Dose 0.48 mg/kg) (N=x)	DCR	Ratio (%)	x.x %
		Complete Response	N	x
		Partial Response	N	x
	Cohort 2 (Dose 1.44 mg/kg) (N=x)	DCR	Ratio (%)	x.x %
		Complete Response	N	x
		Partial Response	N	x
	Cohort 2 Escalation ...	DCR	Ratio (%)	x.x %

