Table will be repeated for each body system.

A similar table will be presented for Part 2

OMO-103-01
Listing 16.2.1.1
Visit Dates
Safety Set

<Study part> - <Cohort>

Subject	Visit	Treatment	Date
xxx	xxxxxxx		xxxxxx
	xxxxxxx	xxxxx	xxxxxx
	xxxxxxx	xxxxx	xxxxxx
	xxxxxxx	xxxxx	xxxxxx
	xxxxxxx		xxxxxx
xxx	xxxxxxx		xxxxxx
	xxxxxxx	xxxxx	xxxxxx
	xxxxxxx	xxxxx	xxxxxx
	xxxxxxx	xxxxx	xxxxxx
	xxxxxxx		xxxxxx
xxx	xxxxxxx		xxxxxx
	xxxxxxx	xxxxx	xxxxxx
	xxxxxxx	xxxxx	xxxxxx
	xxxxxxx	xxxxx	xxxxxx
	xxxxxxx		xxxxxx

Produced: yyyy-mm-ddThh:mm - Page x of y

Programming Note: Date may be split into Start Date and End Date if a visit spans multiple days.

OMO-103-01
Listing 16.2.1.2
Subject Disposition - (1)
All Patients Set

<Study part> - <Cohort>

Subject	Screening Number	Screening Failure	Informed Consent			Informed Re-Consent	
			Date/Time	Version	Physician Obtaining Informed Consent	Date/Time	Version
xxx	xxxx	x	xxxxxxTxx:xx	xxxxx	xxxxx	xxxxxxTxx:xx	xxxxx
xxx	xxxx	x	xxxxxxTxx:xx	xxxxx	xxxxx	xxxxxxTxx:xx	xxxxx
xxx	xxxx	x	xxxxxxTxx:xx	xxxxx	xxxxx	xxxxxxTxx:xx	xxxxx
xxx	xxxx	x	xxxxxxTxx:xx	xxxxx	xxxxx	xxxxxxTxx:xx	xxxxx
xxx	xxxx	x	xxxxxxTxx:xx	xxxxx	xxxxx	xxxxxxTxx:xx	xxxxx
xxx	xxxx	x	xxxxxxTxx:xx	xxxxx	xxxxx	xxxxxxTxx:xx	xxxxx
xxx	xxxx	x	xxxxxxTxx:xx	xxxxx	xxxxx	xxxxxxTxx:xx	xxxxx
xxx	xxxx	x	xxxxxxTxx:xx	xxxxx	xxxxx	xxxxxxTxx:xx	xxxxx
xxx	xxxx	x	xxxxxxTxx:xx	xxxxx	xxxxx	xxxxxxTxx:xx	xxxxx

Produced: yyyy-mm-ddThh:mm - Page x of y

Programming Note: Study part sub-header will be blank for screening failures.

OMO-103-01
Listing 16.2.1.2
Subject Disposition - (2)
All Patients Set

<Study part> - <Cohort>

Subject	Screening Number	Enrollment		Study Completion/Termination			Number of cycles*
		Date	Study Part	Study Completed	Date of Completion/Withdrawal	Reason for Early Withdrawal	
xxx	xxxx	xxxxxx	x	x	xxxxxx		xx
xxx	xxxx	xxxxxx	x	x	xxxxxx		x
xxx	xxxx	xxxxxx	x	x	xxxxxx	xxxxxxxxxx	xxx
xxx	xxxx	xxxxxx	x	x	xxxxxx		xx
xxx	xxxx	xxxxxx	x	x	xxxxxx		x
xxx	xxxx	xxxxxx	x	x	xxxxxx		Xx
xxx	xxxx	xxxxxx	x	x	xxxxxx	xxxxxxxxxx	x
xxx	xxxx	xxxxxx	x	x	xxxxxx		
xxx	xxxx	xxxxxx	x	x	xxxxxx		

* Cycle count includes partial cycles.
Produced: yyyy-mm-ddThh:mm - Page x of y

Programming Note: Study part sub-header will be blank for screening failures.

OMO-103-01
 Listing 16.2.3.1
 Analysis Sets

<Study part> - <Cohort>

Subject	Screening Number	Population	Included (Y/N)
xxx	xxxx	All Patients	x
		Safety	x
		Full Analysis	x
		Per-Protocol	x
xxx	xxxx	x	x
.....			

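### The Part 2 Per Protocol Set requires study completion without defining it, and the only completion status shown would exclude patients because they died

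*SAP*

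**What the plan says.** SAP 6.5 admits to the PPS "All subjects within the FAS who complete the study without a major protocol deviation" judged at the data review meeting (DRM) to bear on an endpoint. It limits per-protocol analysis to the dose expansion groups.

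The PPS feeds two planned results. SAP 11.3 states: "The primary efficacy analysis will be repeated using the PP set". That primary analysis is PFS, and the PPS version is Table 14.2.1.3. The table list in SAP section 14 also gives a PPS version, Table 14.2.2.3, of "Summary of Efficacy parameters, DCR, ORR, OS, TTP, TTR and DOR". The shell note to Table 14.2.2.1 confirms that OS is added for Part 2.

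Completion appears elsewhere only as a disposition status:
- SAP 11.1: "Screening and study completion/termination data (including informed consent information) will also be listed".
- Listing 16.2.1.2 has a yes/no field for study completion beside "Date of Completion/Withdrawal" and a withdrawal reason.
- Table 14.1.1.1 sets completed study against early withdrawal. Under "Reason for Early Withdrawal" it lists death, adverse event and loss to follow-up among others. Progression is not on the list. A programming note carries the table over to Part 2.

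**The concern.** A per-protocol set should differ from the FAS through adherence to the protocol. A completion condition read from the disposition status would make it differ through outcome as well. Death is the OS event and, under the usual definition, a PFS event, so part of the endpoint would decide who is analysed. A gap between PPS and FAS results could then be misread as an effect of protocol adherence.

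The design gives no obvious completion point to fall back on. SAP 3.1 leaves Part 2 cycles unlimited, followed by a 6-month follow-up period.

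**Working it through.** **Text.** SAP section 5 defines product, baseline and protocol deviation, but not completion. Section 6 and the synopsis do not define it either. The phrase in 6.5 can be read as two conditions (complete the study; have no relevant major deviation) or as one (get through the study without such a deviation). On both readings a patient who does not complete is outside the PPS. What counts as not completing therefore matters.

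**Inputs from the documents.** About 18 patients per group (SAP 3.4) and 6 months of follow-up (SAP 3.1). The SAP gives no event or dropout rate, so there is no plan figure to reproduce.

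**Assumptions.** Independent exponential times, rate = ln 2 / median, in months:
- progression, p: median 2 to 3 (base 3)
- death before progression, d: 6 to 24 (base 12)
- death after progression, n: 4 to 9 (base 6)
- adverse-event withdrawal or loss before progression, w: none, 24 or 12 (base none)

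Progression counts as completion, death counts as a PFS event, and follow-up starts at progression. Write m0 = p + d and m = p + d + w.

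**Two versions of the rule.** (A) Only exits before progression are non-completion. (B) Deaths in the 6-month follow-up are non-completion as well.

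**Formulas.**
- Retained, A: p/m. Retained, B: (p/m)·exp(−6n).
- Share of PFS events that are deaths: d/m0.
- Median PFS: all patients ln 2/m0 (censored at withdrawal); PPS ln 2/m.
- 6-month OS, all: exp(−6·m0) + [p/(m0 − n)]·[exp(−6n) − exp(−6·m0)].
- 6-month OS, PPS under A: exp(−6m) + [m/(m − n)]·[exp(−6n) − exp(−6m)].

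**Base case.** p = 0.2310, d = 0.0578, n = 0.1155, w = 0, so m0 = m = 0.2888.
- Retained, A: 0.2310/0.2888 = 0.800, or 14.4 of 18.
- Retained, B: 0.800 × 0.500 = 0.400, or 7.2 of 18.
- Deaths among PFS events: 0.0578/0.2888 = 20%, all removed.
- OS, all: 0.1768 + 1.3333 × (0.5000 − 0.1768) = 60.8%.
- OS, PPS under A: 0.1768 + 1.6667 × 0.3232 = 71.5%.
- Under B, OS at 6 months is 100% by construction.

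**Adding withdrawals (other medians at base).**

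| Withdrawal median | Retained A, of 18 | Retained B, of 18 | OS in PPS (A) | Median PFS in PPS |
|---|---|---|---|---|
| none | 14.4 | 7.2 | 71.5% | 2.40 |
| 24 | 13.1 | 6.5 | 70.1% | 2.18 |
| 12 | 12.0 | 6.0 | 68.7% | 2.00 |

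Median PFS in all patients is 2.40 months throughout.

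**Full range (progression / death before progression / post-progression / withdrawal).**
- Retained, A: lowest at 3/6/any/12, 0.571 × 18 = 10.3; highest at 2/24/any/none, 0.923 × 18 = 16.6.
- Retained, B: lowest 0.571 × 0.354 × 18 = 3.6 (post-progression 4); highest 0.923 × 0.630 × 18 = 10.5 (post-progression 9).
- Deaths among PFS events: 8% (2/24) to 33% (3/6).
- OS excess under A: 0.7 points (3/24/4/12) to 21.6 points (3/6/9/none).

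**Direction for PFS.** With deaths as the only exclusion and independent times, median PFS does not move. If withdrawals also exclude, it shortens, because their censored event-free time is lost. It rises under B if progression and death share prognosis. A separate simulation used a shared gamma frailty (shape 2, mean 1) and set medians, before frailty, for progression and overall death. It gave 1.79 to 2.41 months (medians 2 and 6) and 2.87 to 3.86 months (medians 4 and 6).

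**The case against.** **The record is partial.** SAP 1.1 says the plan is to be read with the protocol and CRF, and only the synopsis of the protocol was available here. A reader might infer that the trial never defines completion. The documents do not support that; they show only that the SAP and synopsis do not. This stands, and it makes the point conditional.

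**Nothing ties the PPS to the disposition flag.** A reader might infer that the plan does exclude patients who die. No section says so. Membership is reviewed at the DRM and agreed before database lock (SAP section 6). Table 14.1.1.1 is a Part 1 shell with a Per Protocol row that 6.5 makes redundant there, and section 15 allows layouts to change. This also stands. But the DRM is given no rule for completion, and the flag is the only completion variable the supplied text offers a programmer.

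**PFS is hardly affected.** A reader might infer that per-protocol PFS would be inflated. In the model above, median PFS is unchanged or shorter unless follow-up deaths exclude and prognosis is shared. The clear effect is on PPS OS, a secondary descriptive result.

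**The size is assumed.** If progression were coded as early withdrawal under the category for other reasons, none of the figures would apply. The SAP text does not say that death is a PFS event. Both points stand.

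**A definition would do instead of a deletion.** Defining completion as follow-up to progression or death would also cure the main fault. Whether early withdrawal or loss to follow-up belongs in a per-protocol set is a legitimate design choice.

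**Conclusion.** The point holds conditionally. SAP 6.5 makes PPS entry depend on an undefined status, and the only version of that status shown treats death as non-completion. If that version is used, PPS OS is too favourable: by about 1 to 22 points at 6 months when only exits before progression exclude, and with no on-study deaths left when follow-up deaths exclude too. The PPS repeat of PFS would lose the 8% to 33% of PFS events that are deaths, with a small or uncertain effect on the median. These sizes rest entirely on the assumed rates, on progression counting as completion, and on death counting as a PFS event.

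A reader might extend this to the trial's main efficacy results. That would be wrong: SAP 11.3 bases them on the FAS and SAF, which have no completion condition. The PPS is supportive and descriptive, and the interim rule in SAP section 8 does not use it. The consequence is modest, but the wording should be corrected before database lock.

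**What to change.** In SAP 6.5, delete the clause on completing the study, so that the PPS is every FAS subject without a major deviation judged at the DRM to be able to affect an endpoint. Then add: *Progression or death does not by itself exclude a subject from the PPS.*

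The sponsor should also state, before database lock, whether adverse-event withdrawal or loss to follow-up excludes a subject. Such subjects can be kept and censored. If the protocol body or CRF already defines completion and the sponsor prefers to keep the condition, 6.5 should cite that definition, after a check that it does not depend on outcome.

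The cost is one clause deleted and a sentence or two added; no new data, tables or deviation criteria are needed. The downside is that the PPS will sit closer to the FAS and its OS may look less favourable.

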**Parts 1 and 2:**

- Patient must have measurable disease as per RECIST v1.1 criteria and documented by CT and/or MRI. NOTE: Lesions to be used as measurable disease for the purpose of response assessment must either:
  - a. not reside in a field that has been subjected to prior radiotherapy, or
  - b. have demonstrated clear evidence of radiographic progression since the completion of prior radiotherapy and prior to study enrolment.
- Tumour biopsy (either from the primary tumour or from metastases) during Screening and during Treatment should be obtained from the patients. Discussion needed with Sponsor if considered not feasible. In Part 1, biopsy obtained only from the 3rd dose level onwards.

Note: In case a patient has had a tumour biopsy in the previous 6 months and a paraffin block is available, a new biopsy does not need to be done at Screening.

- For each patient undergoing pre- and on-treatment biopsies, the identified lesion to be biopsied should not have been previously irradiated and should not be the only lesion being utilised as a measurable-disease target lesion for objective response assessment. Patients must have tumour lesions that can be accessed for biopsy with acceptable clinical risk in the judgement of the Investigator.
- Documented progression on or following the last line of therapy.
- ECOG performance status up to 1.

- Life expectancy of  $\geq 12$  weeks.
- Resolution of all acute, reversible toxic effects of prior therapy or surgical procedure to Grade  $\leq 1$  (except alopecia and peripheral neuropathy to Grade  $\leq 2$ ).
- Adequate organ function as defined by the following criteria:

Haematological:

- a. Neutrophils  $\geq 1,000/\mu\text{L}$
- b. Platelets  $\geq 100,000/\mu\text{L}$
- c. Haemoglobin  $\geq 9$  g/dL

Renal:

- a. Creatinine Clearance (calculated via Cockcroft-Gault Equation)  $\geq 40$  mL/min

Hepatic:

- a. Serum total bilirubin  $\leq 1.5$  ULN or
- b. Direct bilirubin  $\leq$  ULN for patients with total bilirubin  $> 1.5$  ULN
- c. AST/ SGOT and ALT/ SGPT  $\leq 2.5$  ULN or  $\leq 5$  ULN if liver metastases

Coagulation:

- a. INR  $\leq 1.5$
- b. aPTT  $\leq 1.5$  ULN

Chemistry:

- a. Albumin  $> 25$  g/L

- If not postmenopausal or surgically sterile, female patients must be willing to practice at least one highly effective methods of birth control (defined as having a low failure rate) for at least a menstrual cycle before and for 4 months after last study drug administration.

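### The Per Protocol Set serves only Part 2 efficacy outputs, yet a major deviation touching only PK, PD or quality of life can exclude a patient from it

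*SAP*

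**What the plan says.** SAP 6.5 builds the PPS from FAS patients who finish the study free of "a major protocol deviation adjudged in the DRM to potentially affect any endpoint of the study". On its use, the section says "This analysis set will be used for efficacy tables", and on its scope, "A PP analysis will only be performed for the dose expansion groups". The output list in SAP section 14 agrees. It assigns the PPS to PFS (Table 14.2.1.3), to DCR, ORR, OS, TTP, TTR and DOR (Table 14.2.2.3), and to the Kaplan-Meier plots of TTP and TTR (Figures 14.2.6.2 and 14.2.7.2), all marked Part 2 only. SAP 11.3 names the per-protocol run as a repeat of the primary efficacy analysis.

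The study's endpoints go well beyond efficacy. SAP 4.2 states: "The secondary endpoints of the study are the PK profile, as well as tumour response". It also lists QoL questionnaire scores. SAP 4.3 states: "Exploratory endpoints of the study are the PD profile", and adds: "Supporting study variables include biomarkers and Myc expression measurement". The protocol synopsis counts anti-drug antibodies (ADA) and the biopsy markers among the PD parameters.

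SAP 5 has every deviation graded Major or Minor before database lock. On set membership, SAP 11.1 says that "the reason for exclusion from an analysis set will also be presented", and the listing derivations in 11.6.1 repeat that requirement.

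**The concern.** The criterion for leaving the set is wider than the purpose of the set. A patient can have complete scans and a clean RECIST record and still fail the PPS criterion because of a deviation in PK sampling, an on-treatment biopsy or a questionnaire. None of these bears on whether the tumour grew or shrank.

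The per-protocol run is the SAP's pre-specified repeat of the primary PFS analysis. Its value lies in showing whether departures that could distort the tumour outcome change the picture. If it also loses patients for unrelated reasons, a difference between the FAS and PPS results is hard to interpret. The groups are small, the study is open label, and set membership is agreed shortly before lock, when outcomes may already be known. These are reasons to keep the criterion narrow.

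**Working it through.** **1. The plan's own figure.** SAP 3.4 gives up to 24 patients in Part 1 and 18 in each of three Part 2 groups: 24 + 3 × 18 = 78, which matches the stated total. The PPS concerns the 3 × 18 = 54 patients in Part 2.

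**2. What triggers exclusion against what the set is used for.**

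| Endpoint | Where defined | Can trigger PPS exclusion under 6.5 | Reported on the PPS |
|---|---|---|---|
| PFS | SAP 4.1 | Yes | Yes (14.2.1.3) |
| ORR, DCR, TTP, TTR, DOR, OS | SAP 4.2 (tumour response), 11.3 | Yes | Yes (14.2.2.3) |
| PK profile | SAP 4.2 | Yes | No |
| QoL scores | SAP 4.2 | Yes | No (Table 14.2.6 is on the Safety Set) |
| PD profile, biomarkers, Myc expression | SAP 4.3 | Yes | No |

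The last three rows are the mismatch. PK also has its own population, the PK Set in 6.4, with its own major-deviation exclusion, so the PPS need not police PK. SAP 11.4, 14.4 and 14.5 say that the statistics provider will perform no PK or PD analysis, yet those endpoints still help to decide who enters its efficacy set.

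**3. How exclusion happens.** Two conditions must both hold: the deviation is classed Major (SAP 5), and the data review meeting finds that it may affect an endpoint (SAP 6.5). The documents supplied give no criteria for Major and do not place a missed biopsy, PK sample or questionnaire in that class.

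**4. What stays intact.** SAP 11.3 and section 14 also tabulate PFS and the other efficacy endpoints on the Safety Set and the FAS. The PPS deviation rule does not apply there.

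**5. Sensitivity of a group of 18.** Each exclusion removes 1/18 = 5.6% of a group. The documents give no rate of major deviations confined to PK, PD, ADA or QoL, so the rates q below are assumptions, and independence between patients is assumed as well. Expected loss is 18q, and the chance of at least one loss in a group is 1 − (1 − q)^18.

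| Assumed q | Expected loss of 18 | Expected loss of 54 | Chance a group loses at least one |
|---|---|---|---|
| 5% | 0.9 | 2.7 | 60% |
| 10% | 1.8 | 5.4 | 85% |
| 20% | 3.6 | 10.8 | 98% |
| 30% | 5.4 | 16.2 | 99.8% |

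A per-protocol ORR can move either way. With 2 responders among 18, ORR is 11.1% (exact 95% interval 1.4 to 34.7). Removing four non-responders gives 2/14 = 14.3% (1.8 to 42.8). Removing one responder alone gives 1/17 = 5.9% (0.1 to 28.7). These cases show how far a few exclusions can move the figure. They do not predict what will happen.

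**The case against.** The strongest reply is that nobody is removed automatically. A sensible data review meeting would class few missed samples as Major and could decline to exclude a patient whose scans are complete. The protocol is flexible on biopsies: it says that they "during Screening and during Treatment should be obtained from the patients", then allows discussion with the sponsor where one is not feasible, so an agreed omission may not be a deviation at all. This reply stands to the extent that the wording permits exclusion and does not force it. It does not remove the defect, because 6.5 directs the meeting to ask whether any study endpoint may be affected, and for an efficacy set that is the wrong question.

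A second reply is that little depends on the PPS. The main efficacy tables use the FAS and Safety Set, all efficacy analysis is descriptive, and SAP 3.4 has no power calculation. This stands in full and limits the importance of the point.

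A reader might go further and infer that deteriorating patients miss more biopsies, so that the PPS drifts towards longer PFS. One can construct a case: 8 of 18 progression-free at the Cycle 3 scan (44%) becomes 8 of 14 (57%) if four progressors, and nobody else, are excluded. The documents do not support this. They give no link between missed samples and outcome, and the example assumes the bias that it displays. The PFS shell plans no progression-free proportion at that scan. Patients who deteriorate may also already fail the separate requirement in 6.5 to complete the study.

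A reader might also infer that exclusions would be hidden, since the Listing 16.2.3.1 shell has only a yes/no column. That is too strong. SAP 11.1 and 11.6.1 both require the reason, and section 15 allows layouts to change. The shell simply does not match the text.

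**Conclusion.** The point holds in a limited form. Under 6.5 as written, a major deviation affecting only PK, PD or QoL can exclude a patient with valid tumour assessments from the per-protocol PFS, ORR and related Part 2 outputs. The Safety Set and FAS results do not change, and no formal test or error rate is involved. Neither the size nor the direction of the effect can be derived from the documents; the rates in the working are assumptions. The conclusion rests on the plain reading of the criterion and on the endpoint lists in 4.2 and 4.3. It does not depend on how many patients would be excluded. It is worth correcting because the criterion does not fit the only analyses that use it.

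**What to change.** In SAP 6.5, replace the reference to any study endpoint with the efficacy endpoints, spelled out as RECIST tumour assessments, PFS, and survival follow-up for OS. OS must be named because Table 14.2.2.3 reports it on the PPS; a criterion limited to RECIST and PFS would miss it. Add a sentence that deviations affecting only PK, PD or biopsy, ADA or QoL do not exclude a patient from the PPS. PK deviations remain covered by the PK Set in 6.4.

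As a minor alignment, add a column for the reason for exclusion to the Listing 16.2.3.1 shell so that it matches 11.1 and 11.6.1.

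Both changes should be made before database lock and before the data review meeting settles set membership. The cost is two wording changes and one listing column. No new data are needed, and the PPS can only stay the same size or grow.
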